# **3** SAMPLE SIZE

Sufficient participants will be screened to achieve approximately 50 participants randomly assigned to either Chronocort or IRHC (25 participants per treatment arm, regardless of baseline strata), or until a cut-off date of 30 April 2023, whichever is reached first. Individual study sites should not randomize more than 8 participants without first consulting the Sponsor. A sample size of 25 participants per treatment arm will provide at least 80% power to demonstrate non-inferiority of Chronocort to IRHC when the biochemical response rate in the IRHC arm is 40%, the non-inferiority margin is 15%, and the biochemical response rate in the Chronocort arm is 68% using a 1-sided continuity corrected z-test with unpooled variance and a 1-sided alpha of 2.5%. Sample size is calculated using PASS 2022 (v22.0.3).

Note: Basing the sample size calculation on a continuity corrected z-test provides a conservative estimate of sample size relative to the test, based on a logistic model adjusted for stratification factors, which will actually be used.

**Note:** Post-hoc analysis of study DIUR-005 showed that ~40% of participants receiving the control treatment (that is: their pre-randomization treatment) would have been down-titrated by the proposed rules for the current study at four weeks after randomization. Estimating therefore the response rate for the IRHC as 40% and expecting that no participants withdrawn completely from hydrocortisone treatment would qualify for down-titration, the estimated treatment benefit of IRHC is a gain in response rate of 40%. Setting the non-inferiority margin as minus 15% thus retains five eighths of the anticipated treatment benefit of IRHC.

# 4 RANDOMIZATION & UNBLINDING

This is a double-blinded study with 2 treatment arms. The blinded treatment to be taken by a participant will be assigned using an IRT on a 1:1 basis (Chronocort:IRHC). Before the study is initiated, the login information and instructions for use of the IRT will be provided to each site. The randomization list will be generated by the study statistician using a computer-generated central randomization list using balanced blocks. The site will access the IRT at the baseline visit (Day 1) and they will record the randomization number allocated to the participant on the applicable eCRF. Randomization will be balanced within site and stratified by the participant's fludrocortisone replacement status (requires fludrocortisone/does not require fludrocortisone).

Potential bias will be reduced by the following steps:

- Records will be kept of any participants screened, whether or not they enter the study. This will enable an assessment of the representative nature of the participants randomized.
- Both study treatments will be over-encapsulated so that they look the same, so both the participant and the Investigator will not know which treatment group the participant has been randomized to.
- The titration of each participant's dose of study treatment will be the same in both arms and will be based on the adrenal insufficiency checklist and androgen sampling, thus ensuring that opportunities for optimization and control of androgens are the same in both arms.
- The dose titration decisions will be made by an independent blinded physician who will be unaware of the treatment allocation to each participant.
- The treatment packs for each participant will be pre-packed and packs issued by the IRT to ensure that each participant receives the correct number of active and placebo capsules.

After each visit, new supplies will be provided to the participant that contains the same number of capsules as the previous supplies (with placebo capsules masking any changes), regardless of whether the dose was titrated or not, thus ensuring the participant is not aware of any dose changes.

- The primary endpoint is an objective biochemical measure that is not subject to bias.
- Efforts will be made to ensure that all participants remain in the study and are evaluable.
- There will be rigorous monitoring of sites to ensure compliance with all study procedures.
- The statistical analysis plan (SAP) version 1.0 has been completed before screening of the first participant to the study. While it is not reasonable to assume that updates will not occur to the SAP after this point and prior to unblinding of the study, an initial record of planned analysis prior to any participant activity is provided.
- Treatment will be allocated using block randomization. The block size will be determined by the statistician and will not be communicated to the study team.
- To minimize bias whilst the study is ongoing, the study team will remain blinded to aggregated and individual data prior to database lock and any data reviews will use a dummy randomization list with generic labels.
- Participants and Investigators will be requested not to reveal details of the study on social media.

Participants will be allocated an identifying number sequentially per site at the screening visit (Visit 1)

When the participant is randomized at the baseline visit (Visit 2), a separate randomization number will be allocated, which will be used internally for the purposes of treatment allocation and stratum identification. The screening number will still be used for participant identification purposes, so there may be gaps in participant ID numbers for screen failures. Randomization numbers will be assigned sequentially within each stratum and site as soon as participants fully satisfy all of the inclusion and none of the exclusion criteria. Screening and randomization numbers once assigned to a participant must not be re-assigned to another participant. Re-screened participants should be assigned the same participant number as they were assigned during their initial screening visit.

# 5 PLANNED ANALYSES

The SAP supersedes the protocol in case of any differences; a list of any changes from the analyses presented in the protocol is provided in Section 8. The SAP provides a robust plan of the analyses to be conducted for the trial; however, it is recognized that no SAP prepared in advance of the data can be absolutely definitive, and the final Clinical Study Report (CSR) may

contain additional tables or statistical tests if warranted by the data obtained. The justification for any such additional analyses will be fully documented in the final CSR.

The SAP describes all the analyses and summaries that will be performed on the total participant populations. In addition, all analyses and summaries will be repeated on the subgroup of French participants only.

# 5.1 Analysis Sets

Population	Description
Screened Set	All participants who sign the ICF.
Safety Analysis Set (SAF)	All participants who received, either as part of the run-in or post-randomization periods, at least 1 dose of Chronocort or IRHC. Participants will be analyzed according to the treatment they actually received. The SAF is a subset of the Screened Set.
Full Analysis Set (FAS)	All participants with CAH who were randomized into the study and who received at least 1 dose of post randomization study treatment (Chronocort or IRHC). Participants in the FAS will be analyzed according to randomized treatment. The FAS is a subset of the SAF.
Efficacy Evaluable Set (EES)	All participants in the FAS who had Visit 2 and Visit 6 (EOS) 17-OHP and A4 measurements taken at 08:00 hours, and who have no critical protocol deviations that affect the assessment of efficacy. The EES is a subset of the FAS.

For purposes of analysis, the following populations are defined:

Participants excluded from the analysis sets and the reason for their exclusion will be listed, and further details regarding exclusion decisions will be documented during the Data Review Meeting.

# 5.2 Derived Data

This section describes the derivations required for statistical analysis. Unless otherwise stated, variables derived in the source data will not be re-calculated.

#### 5.2.1 Race

Where more than one race category has been selected for a participant, these race categories will be combined into a single category labeled "Multiple Race" in the summary tables. The listings will reflect the original selected categories.

#### 5.2.2 Baseline

Baseline is defined as the last non-missing value (either scheduled, unscheduled or repeat) before the participant receives the first dose of study drug following randomization. Generally, this will be the assessment performed at the Baseline visit (V2).

For androgens / biochemical control status and difference / average of 8:00 and 13:00 17-OHP and A4 results, baseline will be defined as value obtained at Baseline visit (V2).

#### 5.2.3 Duration / Study Day / Time

Study day will be calculated as the number of days from first dose of *study drug* after randomization

- date of event date of first dose of study drug + 1, for events on or after first dose
- date of event date of first dose of study drug, for events before first dose

As the protocol baseline is at Day 1 (i.e. there is no Day 0), any derivation of target day for a scheduled visit and/or applicable visit windows per protocol is in line with this approach. Durations of events related to an anchor point of start of the event will be calculated in a similar manner, replacing date of first dose of study drug with date of start of the event.

# 5.2.4 Quality of Life: SF-36, MAF, EQ-5D

QoL questionnaires (SF-36®, MAF, and EQ-5D-5LTM) will be completed by the participants at Visits 2, 3, 4, 5 and 6 through an electronic data collection tool. No missing data will be allowed by the system and therefore no missing data imputation method will be needed.

The scores for the SF-36 questionnaire for each domain and total will be calculated using the Optum software. The total scores for MAF and EQ-5D will be derived programmatically as per their respective user guides. See Section 11.1 for further details of derivation.

# 5.2.5 Participants Recruited before Implementation of Protocol Version 6.0

The week 28 visit was not scheduled prior to protocol version 6.0. Therefore some participants recruited before the implementation of protocol version 6.0 may be missing the week 28 assessment. In such cases, should the week 34 assessment be available, this will be used for the week 28 assessment. Therefore, where a week 34 assessment is available, no imputation for the missing week 28 assessment will occur. Furthermore, for participants recruited before the implementation of protocol version 6.0, if such a participant does not have a week 28 assessment, but their end of study is between week 16 and week 34, then the end of study is mapped to week 28.

Note, the following conventions will apply for the efficacy and safety analyses.

For efficacy data, all summaries will be presented by all available scheduled visits. In these summaries, week 28 and week 34 will be presented separately. In addition, a further summary, and where applicable analysis, will be performed for week 28 where week 34 assessments are mapped to week 28 as described above. Note, this will be the main analysis for inference.

For safety data, all summaries will be presented by all available scheduled visits. No mapping of week 34 to week 28 will occur.

# 5.2.6 Conventions for Missing and Partial Dates

All rules explained below for partial / missing dates will be followed unless contradicted by any other data recorded on the electronic Case Report Form (eCRF).

All dates presented in the individual participant listings will be presented as recorded on the eCRF (i.e., not completed as per the below rules).

# 5.2.7 Missing / Partial Start / Stop Date of Adverse Events (AE) and Concomitant Medications

Missing and partial start and stop date will be imputed for analysis purposes as follows.

# Partial or missing stop date will be imputed as follows:

If the stop date is completely missing and the event has resolved, or the participant has stopped taking the concomitant medication, the stop date will be imputed as the date of the participant's last clinic visit in the study.

- If only the year is known, the stop date will be imputed as "31-Dec" of that year or as the date of the participant's last clinic visit in the study if in the same year.
- If the month and year are known, the stop date will be imputed as the last day of that month unless the stop date corresponds to the same month as the participant's last clinic visit in which case the date of participant's last clinic visit in the study will be used instead.

#### Missing start date will be imputed as follows:

- If the stop date occurs on or after the start of study drug or the event / concomitant medication is ongoing, the start date will be imputed as the date of the first dose of study drug.
- If the stop date occurs before the start of study drug, the start date of the event / concomitant medication will be imputed as the participant's screening date or the stop date of the event / concomitant medication whichever is the earlier.

#### Partial start date (year present, but month and day missing)

- If the stop date occurs on or after the start of study drug or the event / concomitant medication is ongoing, and the year is the same as the year of first dosing the start date will be imputed as the date of the first dose of study drug. If the year is different from the year of first dosing "01-Jan" will be used.
- If the stop date occurs before the start of study drug, the start date of the event / concomitant medication will be imputed as the "01-Jan" of the same year.

#### Partial start date (month and year present, but day missing)

- If the stop date occurs on or after the start of study drug or the event / concomitant medication is ongoing, the start date will be imputed as the first day of the same month and year unless this partial start date is in same month as the first dose of study drug in which case the date of first dose of study drug will be used.
- If the stop date occurs before the start of study drug, the start date will be imputed as the first day of the month and year of the partial stop date.

If the start time is missing it will be imputed only in the case where the start date of the concomitant medication / event corresponds to the date of the first dose of study drug. The time will be imputed as the same time as the first dose of study drug. In all other cases the time will not be imputed.

# 5.2.8 Missing Last Dates of Study Drug Dosing

If the date of last dose of study drug is completely missing, then the date of last dose of study drug will be taken for analysis purposes as the date when the participant would have run out of study drug assuming full compliance from the date the study drug was last dispensed or the date of participant's last clinic visit in the study or early withdrawal or death whichever the earlier.

If only the month and year of the last dose was recorded, then the date of last dosing will be taken for analysis purposes as the date the participant would have run out of study drug assuming full compliance from the date the study drug was last dispensed, the last day of the month of the recorded last dose or the date of participant's last clinic visit in the study or early withdrawal or death whichever the earlier.

# 5.2.9 Missing Diagnosis Dates

If the month and year are present but the day is missing, for the purpose of calculating duration of disease at baseline/randomization, the diagnosis date will be set to first day of the relevant month. If only the year is recorded the diagnosis date will be set as "01-Jan" for that year.

# 5.2.10 Exposure to Study Drug

The following derivations will be implemented with respect to study drug exposure:

- Total treatment duration (days) = (date of last dose of study drug date of first dose of study drug)+1
- Total glucocorticoid exposure (days) = sum of all periods of glucocorticoid treatment, where each period is calculated as (date of last dose of glucocorticoid in period of treatment – date of start of glucocorticoid treatment during period) +1

# 5.2.11 Inexact Values

In the case where a variable is recorded as "> x", " $\ge$  x", "< x" or " $\le$  x", a value of x will be taken for analysis purposes.

# 5.2.12 Electrocardiogram (ECG) Data

For ECG data recorded on continuous scales, if more than one value is recorded at a time point, the mean value rounded to the integer will be presented. For overall interpretation if more than one value is recorded, the most severe (worst case) of the respective readings will be taken.

#### 5.2.13 Visit Windows

There are no plans to derive visit windows, and visits will be used in the analyses as reported on the eCRF. For participants prematurely withdrawing from the study, the early withdrawal visit will be remapped to the next scheduled visit after the last dose. Note, for participants with an end of study visit between weeks 28 and 34, the end of study visit will be remapped to week 28 for the analysis combining the week 28 and 34 results, see Section 5.2.5. Note, for participants recruited before implementation of protocol version 6.0 (see Section 5.2.5), week 34 assessments used in lieu of week 28 assessments will be used for analysis for the EES, as will any assessments from an end of study visit between week 28 and week 34.

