9.4.2.3. Second Key Secondary Analysis

Assessment	Total daily dose of hydrocortisone at Visit 6 (EOS).
Estimand	The difference (Chronocort arm minus IRHC arm) in the mean total daily dose at Visit 6 (EOS).
Population	The FAS, being representative of the target CAH population.
Outcome Variable	Total daily dose of hydrocortisone at Visit 6 (EOS).
Intercurrent Events	(1) participants who die or withdraw from treatment before Visit 6 (EOS) will have their Visit 6 (EOS) dose imputed within a repeated measures model. (2) participants receiving rescue medication (under 'stress dosing rules') will continue in the study with unchanged procedures, except that Visit 6 (EOS) will be delayed if necessary, to 5 days after the use of rescue medication.
Summary Statistic	The mean total daily dose in each treatment arm at Visit 6 (EOS).
Analysis	The mean difference (Chronocort arm minus IRHC arm) in total daily dose after 28 weeks of randomized treatment is estimated using a repeated measures model with timepoints 10, 16, and 28 weeks after randomization using fludrocortisone use at baseline, biochemical control at baseline, and their interaction as explanatory variables.
Interpretation	Superiority of Chronocort to IRHC with respect to total daily dose after 28 weeks of randomized treatment will be declared if the 95% CI for the difference in means lies wholly below zero, provided that dose superiority of Chronocort to IRHC has been declared.

[figure not shown]
Sensitivity Analysis: The main statistical analysis assumes that the treatment effect is constant over the standard explanatory variables. Sensitivity analyses will investigate whether the treatment effect varies with the explanatory variables.

Other Analyses: Any other analyses of total daily dose, not otherwise specified as a secondary analysis, are supplementary analyses.

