# 5.11.2.3 Second Key Secondary Efficacy Endpoint

Where under the treatment policy strategy, available data occurring on or after the ICE will be analyzed as observed. Data missing at 28 weeks (or any other visit) will be imputed as per Section 5.11.3.3.

**Interpretation:** Superiority of Chronocort to IRHC with respect to total daily dose after 28 weeks of randomized treatment will be declared if the 95% CI for the difference in means lies wholly below zero, provided that biochemical non-inferiority of Chronocort to IRHC has been declared under the primary efficacy objective and dose superiority of Chronocort to IRHC has been declared under the first key secondary efficacy objective.

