# 5.11.3.3 Second Key Secondary Efficacy Endpoint – Total Daily Dose of Hydrocortisone at 28 weeks

For the second key secondary efficacy endpoint, where an ICE occurs, every effort will be taken to ascertain the total daily dose of hydrocortisone (or equivalent) at 28 weeks whether on study or not. Where hydrocortisone is not used, and instead an alternative treatment (such as prednisone, prednisolone or dexamethasone) is received, the dose of the treatment received will be converted to hydrocortisone equivalent as follows [Nebesio et al. 2016]:

- Dexamethasone x 80
- Prednisolone/one x 5

This could occur at pre Run-in Baseline, and for participants that discontinue study treatment.

Where missing data exists for total daily hydrocortisone dose after discontinuation, no explicit imputation will be done.

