# 5.11.5 Key Secondary Efficacy Endpoints and Analyses

The high-level handling approaches for the secondary endpoints are as follows. All observed data for these endpoints will additionally be summarized descriptively by visit, with no imputation.

Endpoint	Analysis Set	Modelling Method	Data Handling
Percentage of Participants Dose	FAS and EES	Logistic Regression	As per Primary efficacy endpoint.
Response after 28 Weeks of Randomized Study Treatment			

Endpoint	Analysis Set	Modelling Method	Data Handling
Mean Total Daily Dose after 28 Weeks of Randomized Study Treatment	FAS and EES	MMRM	Treatment policy strategy for participants who stop treatment before visit 6. Treatment policy strategy for participants whose visit 6 is delayed because of administering rescue medication. Present all visits up to and including V6.

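### For total daily dose, the SAP's visit mapping lets a late leaver's on-study dose stand as an observed week-28 value, with no rule giving precedence to a dose ascertained at 28 weeks

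*SAP*

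**What the plan says.** **Mapping rules.** SAP 5.2.13 (Visit Windows): "For participants prematurely withdrawing from the study, the early withdrawal visit will be remapped to the next scheduled visit after the last dose". SAP 5.2.5 adds a second mapping, limited to people enrolled ahead of protocol version 6.0 who lack a week 28 assessment and whose study ended somewhere from week 16 to week 34. For them, "then the end of study is mapped to week 28". The same section makes the mapped week-28 analysis the one used for inference. Neither section excepts total daily dose.

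**Estimand.** SAP 5.11.5 specifies for this endpoint: "Treatment policy strategy for participants who stop treatment before visit 6". SAP 5.11.2.3 explains that under this strategy "available data occurring on or after the ICE will be analyzed as observed", and continues: "Data missing at 28 weeks (or any other visit) will be imputed as per Section 5.11.3.3". SAP 5.11.3.3 says that after an intercurrent event "every effort will be taken to ascertain the total daily dose of hydrocortisone (or equivalent) at 28 weeks whether on study or not", with conversion factors for prednisolone, prednisone and dexamethasone. It then says that a dose still missing after discontinuation gets no explicit imputation.

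**Protocol.** Section 9.4.2.3 says that participants who die or withdraw from treatment before Visit 6 "will have their Visit 6 (EOS) dose imputed within a repeated measures model". SAP Section 5 says that the SAP supersedes the protocol and that Section 8 lists the changes. Section 8 lists none on this point.

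**The concern.** The estimand asks what dose the participant was taking at week 28. The mapping rule supplies the dose at the time of leaving, which may be up to 12 weeks earlier. The two can differ: Protocol 7.1 returns participants who discontinue study treatment to their pre-study glucocorticoid and dose, which need not equal a study dose of 15 to 30 mg.

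A mapped value also counts as observed. It therefore bypasses the model-based handling in Protocol 9.4.2.3 and competes with any dose ascertained under SAP 5.11.3.3. Two programmers could each follow the SAP and enter different week-28 doses for the same person. Total daily dose is a confirmatory superiority endpoint, third in the fixed sequence, so its week-28 value should be uniquely defined before unblinding.

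**Working it through.** **1. The plan's own figure.** The SAP gives no power or SD for total daily dose. Its only power statement is for the primary test (40% v 68%, margin 15%, 25 per arm, continuity corrected). It reproduces: Φ[(0.43 − 1/25)/√((0.40×0.60 + 0.68×0.32)/25) − 1.96] = Φ[0.39/0.1353 − 1.96] = 82.2%, consistent with at least 80%. This point does not change it. It is used here only for n = 25 per arm.

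**2. Tracing one participant who leaves the study after Visit 5.**
- Visit 5 is week 16, and the next clinic visit is Visit 6 at week 28 (Protocol 8.1.7). The model's timepoints are weeks 10, 16 and 28, so the mapped visit takes the week-28 place.
- Withdrawal assessments are due within 48 hours of the last study dose, and the visit records doses over the previous 24 hours and during the visit (Protocol 8.1.10). The value is mainly the on-study dose.
- If a 28-week dose is later ascertained off study, nothing says that it replaces the mapped one. SAP 5.2.13 uses visits as reported, and SAP 5.2.14 generally disregards unscheduled post-baseline assessments. SAP 5.2.5 does not say whether an ascertained dose counts as a week 28 assessment.

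**3. Shift per participant with an ascertained dose.** Let gap = dose taken at week 28 minus mapped dose. The arm mean shifts by gap/25: 5/25 = 0.2 mg, 10/25 = 0.4 mg, 20/25 = 0.8 mg. On the SAP's factors, a 10 mg gap is 10/5 = 2 mg of prednisolone or 10/80 = 0.125 mg of dexamethasone. With covariate adjustment (assumed 80% on fludrocortisone, 40% in control; 2,000 random covariate sets), a 10 mg gap shifts the treatment difference by a median of 0.40 mg (95% range 0.17 to 0.62).

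**4. Scale.** 95% CI half-width = 2.0106 × SD × √(2/25). For an assumed SD of 4, 5 or 6 mg this is 2.27, 2.84 or 3.41 mg, so 0.4 mg is 0.18, 0.14 or 0.12 of it.

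**5. Direction.** This illustration rests wholly on assumptions. Each of three titration visits brings a 5 mg reduction with probability 0.55 (Chronocort) or 0.40 (IRHC). Three Chronocort and no IRHC participants leave after Visit 5, before that visit's titration takes effect. Expected on-study week-28 means are 30 − 15×0.55 = 21.75 and 30 − 15×0.40 = 24.00 mg, a difference of −2.25. The leavers' mapped dose is 30 − 10×0.55 = 24.50.

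| Week-28 value for the three leavers | Difference, mg |
|---|---|
| Missing, handled by the model | about −2.25 |
| Mapped visit | −2.25 + 3×(24.50 − 21.75)/25 = −1.92 |
| Actual, if 30 mg off study | −2.25 + 3×(30 − 21.75)/25 = −1.26 |
| Actual, if 40 mg off study | −2.25 + 3×(40 − 21.75)/25 = −0.06 |
| Actual, if 20 mg off study | −2.25 + 3×(20 − 21.75)/25 = −2.46 |

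Simulation (4,000 repeats) agrees to within 0.02 mg. Mapping favours Chronocort at an off-study dose of 30 or 40 mg and disfavours it at 20 mg. With two leavers per arm and 30 mg off study, the simulated differences are −2.10 (actual) and −2.22 (mapped), only 0.12 mg apart.

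**6. No dose ascertained.** In a simulated three-visit unstructured model (25 per arm, assumed correlations 0.70 to 0.85), leaving week 28 missing instead of mapped changed the difference by −0.002, 0.013 and 0.007 mg on average for SD 4, 5 and 6. The spread per participant was 0.085 to 0.153 mg (SD). The near-zero average depends on the assumptions: in step 5, where leavers miss the last titration, the missing route lies 3×2.75/25 = 0.33 mg further from the actual-dose result at 30 mg than the mapped route.

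**The case against.** The strongest reply is that SAP 5.11.3.3 is written for this variable after an intercurrent event, whereas 5.2.13 is a general visit-labelling rule, and the specific rule should govern. That is a natural reading, and it rules out saying flatly that the SAP will enter the wrong dose. But the precedence is not written, and 5.2.13 as it stands produces a value.

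Other limits also stand:
- SAP 5.2.13 names withdrawal from the study, not stopping treatment while staying in. Protocol 8.1.10 uses Visit 6 for both the treatment-withdrawal assessment and the 28-week visit, so that route is unclear rather than wrong.
- Routine records may not reach week 28 for people who have left. Protocol 6.5 covers medication received during the study, the Schedule of Activities has no concomitant-medication entry at Call T6.1, and SAP 5.12.3.2 classifies later medication without collecting it. Ascertainment rests on the commitment in 5.11.3.3.
- The two SAP statements on imputation can both mean implicit handling by the model. SAP Section 9 records that multiple imputation was dropped for this endpoint, so this is loose wording, not a contradiction.
- Because the SAP supersedes the protocol, the departure from Protocol 9.4.2.3 is at most an omission from Section 8.

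A reader might infer that the mapping biases the result towards Chronocort, or that leaving week 28 missing is closer to the estimand. The documents support neither. The sign depends on doses and counts they do not give. Handling under missing at random is not treatment policy either, since it borrows from participants still on treatment.

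**Conclusion.** Wrong as written, as an internal conflict, and minor. For a participant who leaves after Visit 5, the general mapping rules and the endpoint-specific rule point to different week-28 doses, and the SAP does not rank them.

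Where a 28-week dose is ascertained, the shift is 0.2 mg in an arm mean per affected participant per 5 mg of gap. Equal numbers and gaps in both arms cancel. Where none is ascertained, the choice between mapped and missing changes the estimate by about 0 on average under the assumptions of the three-visit model. Withdrawal counts, gaps, SDs, correlations and direction are all assumptions.

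A reader might extend this to the primary endpoint or to dose response. That does not follow: withdrawal from treatment counts as non-response under the composite strategy (SAP 5.11.2.1 and 5.11.2.2), so neither is materially affected.

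**What to change.** For total daily dose only:

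1. In SAP 5.2.13, 5.2.5 and 5.11.3.3, state that a 28-week hydrocortisone-equivalent dose ascertained under 5.11.3.3 takes precedence over any remapped visit of a participant who stopped study treatment before week 28, whether or not that participant stays in the study.
2. If none is ascertained, do not treat the remapped visit as an observed week-28 value. Leave week 28 missing for the repeated measures model, in line with Protocol 9.4.2.3 and the no-explicit-imputation text. Acknowledge that this fallback assumes missing at random and is not itself treatment policy.
3. Align the imputation wording in 5.11.2.3 with item 2.

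A sensitivity analysis to the missing-at-random assumption is optional. The cost is about three sentences of SAP text and one derivation, plus the ascertainment effort to which 5.11.3.3 already commits. The drawback is that the withdrawal-visit dose, possibly the only visit record after the Visit 5 titration, is not used at week 28. The estimate may move in either direction.
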